9.2 Handling of Missing Data

Missing data could occur due to various reasons, including missing visits/assessments, early withdrawal from the clinical trials, or missing due to COVID-19 infection or logistic restrictions during the pandemic. Assessments on or after any intercurrent event will be handled as specified in Section 8.0.

The COVID-19 pandemic is interfering with the conduct of many ongoing trials, with potential impacts on treatment duration and the collection, analysis, and the interpretation of clinical trial data. For example, some scheduled visits may be missed due to self-quarantine or local government restrictions on travel; some visits may also be delayed

or canceled due to healthcare resource constraints during the pandemic. Impacted visits due to COVID-19 will be recorded in the database. The probability of having missed visits and missing data due to COVID-19 infection or logistical restrictions related to the COVID-19 pandemic can be reasonably assumed to be unrelated to the unobserved values. Therefore, for the purpose of statistical analysis, it is reasonable to assume that these missing data are missing at random (MAR) and the statistical models that require MAR assumption are appropriate. The intent is to provide reliable estimates of the treatment effects under the scenario without the impact of COVID-19 pandemic.

Missing data for the efficacy analyses will be handled using the methods described below.

9.2.1 Categorical Endpoints

For binary efficacy endpoints other than the occurrence of hospitalization and the occurrence of CD-related surgery, missing data will be handled using the following approaches:

- The primary approach for handling missing data in the analysis of binary endpoints will use **Non-Responder Imputation (NRI)** while incorporating Multiple Imputation (MI) to handle missing data due to **COVID-19 (NRI-C)**.
 - The NRI-C will categorize any subject who does not have an evaluation during a pre-specified visit window (either due to missing assessment or due to early withdrawal from the study) as a non-responder for the visit. The only exception is that missing data due to COVID-19 infection or logistical restriction will be handled by MI. At each visit, subjects will be characterized as responders or non-responders based on MI imputed values if missing due to COVID-19; otherwise, subjects will be considered as non-responders for missing due to other reasons in the NRI-C approach. In addition, at and after the CD-related corticosteroids intercurrent event (see Section 8.2) and on/after the date of initiation of CD-related confounding medications after premature discontinuation of study drug (see Section 8.1), subjects will be considered as non-responders and will not be imputed by MI.

- A sensitivity analysis for binary endpoints will use **NRI** with **No** special data handling for missing due to **COVID-19** (NRI-NC).
 - NRI-NC will be performed in the same way as NRI-C without the exception above. Missing due to COVID-19 infection or logistical restriction will also be counted as non-responders. Subjects on or after the occurrence of the CD-related corticosteroids intercurrent event and on/after the date of initiation of CD-related confounding medications after premature discontinuation of study drug will still be considered as non-responders. This is the same method as "NRI" as defined in the protocol.
- Details on MI method in NRI-C are described below:
 - Markov Chain Monte Carlo (MCMC) will be first applied to augment data into monotonic missing pattern (where applicable) and PROC MI will be used to generate 30 datasets using the regression method. If the binary endpoints are derived from the continuous variables, PROC MI will be applied to the continuous variables. The variables to be included in the imputation model are: treatment group, randomization stratification factors (baseline steroid use (Yes, No), endoscopic disease severity (SES-CD < 15, ≥ 15) and number of prior biologics with inadequate response or intolerance (≤1, > 1)), age, gender, weight, baseline measurement (if applicable) and post-baseline measurements at each visit up to the end of the analysis period. The random seed for MCMC and the random seed for PROC MI are specified in [Appendix I](#). The imputed post-baseline measurements will be rounded to the same precision as the observed data before the determination of responder status. Subjects will be characterized as responders or non-responders based on MI imputed data. Using the CMH model adjusted by randomization stratification factors, the endpoints will be analyzed using each of the 30 imputed datasets. SAS PROC MIANALYZE will be used to generate the final inferences of the risk difference between upadacitinib group and placebo group, using Rubin's rule³. Note that measurements will be set to missing for 1) at or after the occurrence of the CD-related corticosteroids intercurrent event 2) on/after the date of initiation of CD-related confounding medications after premature discontinuation of study drug

before applying MI. After the MI imputation, an NRI override will be implemented for missing values 1) missing values due to reasons other than COVID-19 infection or logistic reasons, or 2) at or after the occurrence of the CD-related corticosteroids intercurrent event or 3) on/after the date of initiation of CD-related confounding medications after premature discontinuation of study drug, that is, regardless of MI imputed values, subjects satisfying 1) or 2) or 3) will be considered as "non-responder" for binary efficacy endpoints.

For binary efficacy endpoints regarding the occurrence of hospitalization and the occurrence of CD-related surgeries, missing data will be handled using the following approaches.

- As observed analysis (AO): The AO analysis will not impute values for missing evaluations, and thus a subject who does not have an evaluation on a scheduled visit will be excluded from the AO analysis for that visit. AO will include all values collected in the study.

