- The difference in the proportion of subjects achieving clinical remission per PROs at Week 12 regardless of premature discontinuation of study drug but before initiation of CD-related confounding medications (See Section 8.1), and without initiation or dose escalation of CD-related corticosteroids (See Section 8.2) in the upadacitinib 45 mg QD and placebo groups in the ITT population (EU/EMA regulatory purposes).
- The difference in the proportion of subjects achieving clinical remission per CDAI at Week 12 regardless of premature discontinuation of study drug but before initiation of CD-related confounding medications (See Section 8.1), and without initiation or dose escalation of CD-related corticosteroids (See Section 8.2) in the upadacitinib 45 mg QD and placebo groups in the ITT population (US/FDA regulatory purposes).
- The difference in the proportion of subjects achieving endoscopic response at Week 12 regardless of premature discontinuation of study drug but before initiation of CD-related confounding medications (See Section 8.1), and without initiation or dose escalation of CD-related corticosteroids (See Section 8.2) in the upadacitinib 45 mg QD and placebo groups in the ITT population.

Secondary Efficacy Objectives

The secondary efficacy objectives of the Study M14-431 are to demonstrate higher efficacy of treatment with upadacitinib 45 mg QD when compared to placebo during the 12-week double-blind induction period (Part 1) with respect to the ranked secondary endpoints specified in Section 3.2 in subjects with moderately and severely active CD who have inadequately responded to or are intolerant to biologic therapy. The secondary efficacy objectives will be assessed based on ITT population.

Hypotheses corresponding to the ranked secondary efficacy objectives and endpoints are: for each of the ranked secondary endpoints except occurrence of hospitalizations due to CD during Part 1 (Section 3.2), greater proportion of subjects with improvement (or greater mean change from Baseline for continuous endpoints) is achieved with upadacitinib 45 mg QD group when compared to that of placebo. Hypothesis

corresponding to occurrence of hospitalizations due to CD during Part 1 is: smaller proportion of subjects experience at least one occurrence of hospitalizations due to CD during Part 1 with upadacitinib 45 mg QD group when compared to that of placebo.

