8.1 Intercurrent Event 1 (IE1): Premature Discontinuation of Study Drug

Following the intent-to-treaty (ITT) principle, a treatment policy strategy will be used to handle the IE1. Data collected on/after premature discontinuation of study drug will be used for all efficacy endpoints.

The only exception is when data are collected on/after the date subjects switching to other treatment for CD, which will be handled as follows:

- **Binary endpoints other than the occurrence of hospitalization and/or the occurrence of CD-related surgery endpoints:** A composite strategy will be used in the efficacy analysis: the subject will be considered as non-responders at all visits on/after the initiation of other CD-related confounding medications.
- **Binary endpoints regarding the occurrence of hospitalization and/or the occurrence of CD-related surgery endpoints:** A treatment policy strategy will be used regardless.
- **Continuous endpoints:** A hypothetical strategy will be used in the efficacy analysis. Data collected on/after the initiation of other CD-related confounding medications will not be used in the analysis. Efficacy analysis will be handled by using corresponding statistical models (e.g., the Mixed-Effect Model Repeated Measurement [MMRM] model).

The CD-related confounding medications include:

- Biologics approved for CD (Adalimumab, Certolizumab, Infliximab, Ustekinumab, Vedolizumab, Natalizumab)
- Any investigational compound
- Systemic corticosteroids or locally acting steroids, rectal corticosteroid
- Immunosuppressants (azathioprine, mercaptopurine, methotrexate, tacrolimus, cyclosporine)

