8.2 Intercurrent Event 2 (IE2): CD-Related Corticosteroids

The CD-related corticosteroids intercurrent event is defined as follows.

In Part 1/Part 2:

1. subjects not on CD-related corticosteroids (systemic or oral locally acting corticosteroids for CD) at baseline which are then initiated during Part 1/Part 2
2. a) subjects on CD-related corticosteroids at baseline who have dosages increased to greater than the prednisone equivalent dose taken at baseline until Week 10 or
b) subjects with any dose increase in CD-related corticosteroids between Week 10 and Week 12
3. subjects not on rectal corticosteroid at baseline who initiated rectal corticosteroids during Part 1/Part 2, regardless of rectal corticosteroid dose
4. subjects on rectal corticosteroids at baseline who have the dosage increased to greater than the dose taken at baseline during Part 1/Part 2;
5. subjects on rectal corticosteroids at baseline and initiated different rectal corticosteroids during Part 1/Part 2, regardless of rectal corticosteroid dose

In Part 3:

1. subjects not on CD-related corticosteroids (systemic or oral locally acting corticosteroids for CD) at baseline which are then initiated during Part 3
2. a) subjects on CD-related corticosteroids at baseline who have dosages increased to greater than the prednisone equivalent dose taken at baseline and Week 12 until Week 22 or
b) subjects with any dose increase in CD-related corticosteroids between Week 22 and Week 24

3. subjects not on any rectal corticosteroid at baseline and during Part 1/Part 2 who initiated rectal corticosteroids during Part 3, regardless of rectal corticosteroid dose
4. subjects on rectal corticosteroids at baseline or during Part 1/Part 2 who have dosage increased to greater than the dose taken at baseline during Part 3;
5. subjects on rectal corticosteroids at baseline or during Part 1/Part 2, and initiated different rectal corticosteroids during Part 3, regardless of rectal corticosteroid dose

The time point of the CD-related corticosteroids intercurrent event is defined as the date when one of the scenarios above occurs for a subject.

Binary endpoints other than the occurrence of hospitalization and/or the occurrence of CD-related surgery endpoints: A composite strategy will be used in the efficacy analysis: the subject will be considered as non-responders at all visits on/after the initiation of CD-related corticosteroids.

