9.2.3 Additional Analyses

In addition, As Observed (AO) and tipping point analysis will be performed as supplementary and sensitivity analyses, if appropriate, for categorical or continuous endpoints.

- AO: The AO analysis will not impute values for missing evaluations, and thus a subject who does not have an evaluation on a scheduled visit will be excluded from the AO analysis for that visit. AO will include all values collected in the study.
- Tipping Point Analysis for Binary Endpoints
The tipping point analyses are two-dimensional, i.e., assumptions about the missing outcomes on each of the upadacitinib group and the placebo group can vary independently. The response rate among those subjects with missing response is assumed to be p_0 for placebo group and p_1 for upadacitinib group, and the response rate p_0 and p_1 systematically vary from 0% to 100% by every 10% respectively. Given a set of (p_0, p_1) , the subjects with missing response will be randomly assigned as responders or non-responders using binomial distribution to generate 30 imputed datasets, and the same CMH method used for the primary analysis will be performed on each of the imputed datasets to obtain the results for each comparison between the upadacitinib group versus the placebo group. SAS PROC MIANALYZE will be used to generate the final inferences of the risk difference between upadacitinib group and placebo group, using Rubin's rule.³

If one pair of (p_0, p_1) is found to reverse the study result interpretation in terms of p-value larger than 0.05, then the (p_0, p_1) is identified as the tipping

point. The results for a grid of (p0, p1) combinations are provided in tabular format. Note that missing data 1) on or after the occurrence of the CD-related corticosteroids intercurrent event or 2) on/after the date of initiation of CD-related confounding medications after premature discontinuation of study drug will be considered as non-responders and will not be imputed in the tipping point analysis.

- Tipping Point Analysis for Continuous Endpoints

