9.3.2 Primary Analysis of Co-Primary Efficacy Endpoints

The attributes of the estimands corresponding to the co-primary efficacy endpoints are summarized in [Table 1](#).

The co-primary endpoints will be analyzed between upadacitinib group and placebo group using the CMH test, stratified by the randomization factors (baseline steroid use (Yes, No), endoscopic disease severity (SES-CD < 15, \geq 15) and number of prior biologics with prior inadequate response or intolerance (\leq 1, > 1)) based on ITT1.

Table 1. Summary of the Estimand Attributes of the Co-Primary Efficacy Endpoints

Estimand Label	Attributes of the Estimand				Statistical Summary
	Treatment	Endpoint	Population	Intercurrent Events	
Co-Primary 1a	Upadacitinib 45 mg QD vs. placebo	Achievement of clinical remission per PROs at Week 12 (for EU/EMA)	ITT1 population (Subjects who were randomized and received at least one dose of study drug in Part1)	IE1: premature discontinuation of study drug IE2: Initiation or dose escalation of CD-related corticosteroids All data after IE1 will be used until initiation of CD-related confounding medications All subjects will be considered as non-responders at or after IE2	Difference in the proportion of subjects achieving clinical remission per PROs
Co-Primary 1b	Upadacitinib 45 mg QD vs. placebo	Achievement of clinical remission per CDAI at Week 12 (for US/FDA)	ITT1 population (Subjects who were randomized and received at least one dose of study drug in Part1)	IE1: premature discontinuation of study drug IE2: Initiation or dose escalation of CD-related corticosteroids All data after IE1 will be used until initiation of CD-related confounding medications All subjects will be considered as non-responders at or after IE2	Difference in the proportion of subjects achieving clinical remission per CDAI

Table 1. Summary of the Estimand Attributes of the Co-Primary Efficacy Endpoints (Continued)

Estimand Label	Attributes of the Estimand				Statistical Summary
	Treatment	Endpoint	Population	Intercurrent Events	

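### Starting a prohibited biologic, investigational compound or immunosuppressant while still on study drug does not count as non-response in the co-primary analysis, although an on-drug steroid start does (SAP 8.0, 9.2.1, 9.2.3)

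*SAP*

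**What the plan says.** SAP 8.0 names two intercurrent events: stopping study drug early (IE1), and starting or escalating CD-related corticosteroids (IE2).

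Under IE1 the SAP keeps data collected after study drug stops, with one exception for subjects who move to another Crohn's treatment. For most binary endpoints, 8.1 then says "the subject will be considered as non-responders at all visits on/after the initiation of other CD-related confounding medications". For continuous endpoints, data from that point are not used. The medications listed are biologics approved for Crohn's disease, any investigational compound, steroids, and immunosuppressants. Table 1 gives the same rule for the co-primary endpoints: "All data after IE1 will be used until initiation of CD-related confounding medications". Table 2 repeats it for the ranked secondary endpoints other than hospitalisation.

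The working rules in 9.2.1 state the order of events explicitly. For NRI-C: "on/after the date of initiation of CD-related confounding medications after premature discontinuation of study drug (see Section 8.1), subjects will be considered as non-responders". NRI-NC, the step that sets values to missing before multiple imputation, and the override after imputation carry the same condition. So does the binary tipping point analysis in 9.2.3: "confounding medications after premature discontinuation of study drug will be considered as non-responders and will not be imputed in the tipping point analysis".

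IE2 has no such condition. Its first scenario is "subjects not on CD-related corticosteroids (systemic or oral locally acting corticosteroids for CD) at baseline which are then initiated during Part 1/Part 2", and the subject is a non-responder from then on, whether or not study drug continues.

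The co-primary estimands in 2.1 are worded "regardless of premature discontinuation of study drug but before initiation of CD-related confounding medications", with a cross-reference to 8.1.

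**The concern.** A subject who stays on blinded study drug, starts infliximab or azathioprine in Part 1 and is in remission at Week 12 meets neither intercurrent event. The value is observed, so nothing is imputed or overridden, and the subject is a success for the randomised arm. A subject who stays on study drug and starts prednisone is a failure. The SAP puts both drug groups on one list of confounding medications and gives no reason to treat them differently.

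The situation can arise. The protocol prohibits the biologics, investigational drugs and most of the immunosuppressants (5.2.3.3) and new starts of methotrexate (5.2.3.2.1), and use of a prohibited treatment is a reportable deviation (7.0). But 5.4.1 ties discontinuation of study drug after such a start to whether continuing would place the subject at risk, so it is not automatic.

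At stake is what a co-primary responder means: success of the randomised treatment, or success of that treatment plus another active Crohn's therapy.

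**Working it through.** **Four subjects, each with an observed Week 12 response, under 9.2.1**

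| Course in Part 1 | Event under 8.0 | Week 12 status |
|---|---|---|
| Stops study drug, starts nothing | IE1 | observed value: success |
| Stops study drug, then starts a listed biologic | IE1 with exception | non-responder |
| Stays on study drug, starts a CD-related steroid | IE2 | non-responder |
| Stays on study drug, starts a listed biologic, investigational compound or immunosuppressant | none | observed value: success |

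The last row is the gap. No planned analysis counts that subject as a failure. NRI-NC repeats the condition. The tipping point analysis varies missing outcomes only. The as-observed analysis uses all data by design. The per-protocol analysis (9.3.4) may exclude the subject.

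**Planned power (SAP 2.4).** Inputs: 330 upadacitinib and 165 placebo subjects, Fisher's exact test, two-sided 0.05. Exact enumeration gives:
- remission per PROs, 29% vs 12%: 99.4%
- remission per CDAI, 40% vs 20%: 99.6%
- endoscopic response, 25% vs 10%: 98.7%

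All three agree with the stated figure of at least 95%.

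**Effect of one affected responder.** 1/330 = 0.30 points in the upadacitinib arm; 1/165 = 0.61 points in the placebo arm.

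**Illustrations.** The documents give no initiation rate, so what follows is assumption. Let q be the share of one arm that starts such a drug on treatment, and r the response rate of starters, set to the planned upadacitinib rate (full) or half of it. Planned rates are taken to hold when starters count as non-responders, so the affected arm's rate becomes planned rate + q × r.

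Placebo-only starts. Example: endoscopic, q = 5%, full rate: 0.10 + 0.05 × 0.25 = 0.1125, compared with 0.25.

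| Power | Planned | q = 1%, full / half | q = 2%, full / half | q = 5%, full / half |
|---|---|---|---|---|
| PROs | 99.4% | 99.2% / 99.3% | 99.0% / 99.2% | 98.0% / 98.9% |
| CDAI | 99.6% | 99.5% / 99.5% | 99.3% / 99.5% | 98.4% / 99.2% |
| Endoscopic | 98.7% | 98.3% / 98.5% | 97.9% / 98.3% | 96.2% / 97.7% |

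At the full rate and with no upadacitinib starters, power falls below 95% only from 11 (endoscopic), 16 (PROs) or 17 (CDAI) placebo starters of 165.

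Upadacitinib-only starts with no true effect. Both arms sit at the planned placebo rate and the upadacitinib rate is raised by q × r. Example: PROs, q = 5%, full rate: 0.12 + 0.05 × 0.29 = 0.1345, compared with 0.12. Chance of a significant result favouring upadacitinib, per endpoint:

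| | q = 0 | q = 2%, full / half | q = 5%, full / half |
|---|---|---|---|
| PROs | 2.0% | 3.0% / 2.4% | 5.3% / 3.3% |
| CDAI | 2.1% | 3.4% / 2.7% | 6.5% / 3.8% |
| Endoscopic | 2.0% | 2.9% / 2.4% | 4.9% / 3.2% |

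Both co-primary endpoints must be significant, so the joint chance is lower. If q and r are the same in both arms, the difference does not change.

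**The case against.** The strongest reply is that the SAP agrees with itself. The 8.1 rule stands under the IE1 heading, as an exception for subjects who change treatment. Tables 1 and 2 attach the cut-off to data after IE1. The 2.1 wording cites 8.1 for its meaning, and 9.2.1 and 9.2.3 state the same rule. On that reading, using the observed value of an on-drug starter is simply treatment policy for a protocol deviation.

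Most of this stands. A reader might infer that 9.2.1 contradicts the estimand, because the clause in 2.1 and the sentence in 8.1 carry no explicit limit to starts after discontinuation, and because 9.2 says "Assessments on or after any intercurrent event will be handled as specified in Section 8.0". The documents do not support that stronger reading: both texts take their scope from IE1, and an on-drug non-steroid start is not a listed intercurrent event. But the reply does not supply a strategy for on-drug starts or explain why on-drug steroids are treated differently.

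The second reply is that the effect is limited. The drugs are prohibited, deviations are tabulated by treatment group, and an affected subject must start within 12 weeks, stay on study drug and respond at Week 12. This also stands and bears on size. However, excluding such subjects in a per-protocol analysis is not the same as counting them as failures in the primary analysis.

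**Conclusion.** The gap is real and sits in the primary analysis of the co-primary endpoints. The rule as written can credit the randomised arm with a response obtained while another active Crohn's therapy was being taken. The 2.1 wording leaves some doubt whether that was intended.

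The effect is probably small and its direction is unknown: it depends on which arm has more on-drug starts, and the documents give no rate. Under the assumed 5% placebo-only starts, power stays at or above 96.2%. Under assumed upadacitinib-only starts of 2% or 5% with no true effect, the per-endpoint chance of a false positive favouring upadacitinib rises from 2.0–2.1% to 2.9–3.4% or 4.9–6.5% at the full response rate, and to 2.4–2.7% or 3.2–3.8% at half.

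A reader might infer from these figures that the trial is underpowered or biased towards upadacitinib. The documents support neither: the figures assume starts in one arm only, and nothing in the documents gives reason to expect that. The case for a change rests on having one unambiguous responder definition. The effect on continuous endpoints was not calculated; they are included because 8.1 and Table 2 frame their data exclusion in the same way.

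**What to change.** In SAP 8.0/8.1, 9.2.1, 9.2.3 and Tables 1 and 2, apply the existing composite non-responder rule from initiation of any listed non-steroid CD-related confounding medication, whether or not study drug has stopped. Apply the existing 8.1 data exclusion for continuous endpoints in the same way, and align the 2.1 estimand wording.

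Keep the rest as it is: on-drug steroids stay under IE2, stable baseline methotrexate is not an initiation, treatment policy remains for the hospitalisation and CD-related surgery endpoints, and the as-observed analysis is unchanged.

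The cost is SAP wording and one flag from concomitant-medication data already collected, with no extra analysis run. The downside is that response rates may be slightly lower, because a starter who would have responded to study drug alone is also counted as a failure. This concerns data handling only and changes nothing in the management of subjects.
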